10.1.3. Response Criteria

On-site assessments will include the assessment of:

- Target and non-target tumor responses
- Objective response

The above assessments will be made as per the time points identified in [Section 9.17](#), Solid Tumor Assessments/Scans.

10.1.3.1. Target and Non-Target Response Assessments

Assessments will be based on the definitions below.

TARGET LESIONS	
Lesions Response:	Definition:
Complete Response (CR)	The disappearance of all target lesions. Any pathological lymph nodes must have reduction in short axis to < 10 mm.
Partial Response (PR)	At least a 30% decrease in the sum of diameters of the target lesions, taking as a reference the baseline sum diameters.
Progressive Disease (PD)	At least a 20% increase in the sum of diameters of the target lesions, taking as a reference the smallest sum on study, including the baseline sum. In addition to the relative increase of 20%, the sum must also demonstrate an absolute increase of at least 5 mm. Definitive new lesion presence also indicates progression.
Stable Disease (SD)	Neither sufficient shrinkage to qualify for PR nor sufficient increase to qualify for PD, taking as a reference the smallest sum diameters while on study.

NON-TARGET LESIONS	
Lesions Response:	Definition:
Complete Response (CR)	Disappearance of all non-target lesions and normalization of tumor marker level. All lymph nodes must be non-pathological in size (< 10-mm short axis)
Non-CR/Non-PD	Persistence of one or more non-target lesion(s) and/or maintenance of tumor marker level above the normal limits.
Progressive Disease (PD)	Unequivocal progression of existing non-target lesions (see definition below).

Progression in Non-target Disease:

There must be an overall level of substantial worsening in non-target disease such that, even in the presence of stable disease (SD) or partial response (PR) in target disease, the overall tumor burden has increased sufficiently to merit discontinuation of therapy.

Because worsening in non-target disease cannot be easily quantified, a useful test that can be applied when assessing patients for unequivocal progression is to consider if the increase in overall disease burden based on the change in non-measurable disease is comparable in magnitude to the increase that would be required to declare progressive disease (PD) for measurable disease (i.e., an increase in tumor burden representing an additional 73% increase in “volume” [which is equivalent to a 20% increase in the diameter of a measurable lesion]).

10.1.3.1.1. Additional Criteria to Consider When Making Tumor Response Assessments

When effusions are known to be a potential adverse effect of treatment, cytological confirmation of the neoplastic origin of any effusion that appears or worsens during treatment when the measurable tumor has met criteria for response or SD is not mandatory, but might be performed to differentiate between response (or SD) and PD when substantial change of effusion and or ascites is noted.

If a patient is discontinued from the study before PD occurs and receives local or regional palliative radiotherapy during the follow-up period, the irradiation site must be omitted from the response assessment of the patient; however, if the site is observed to demonstrate disease progression, this case should be judged as PD.

For equivocal findings of progression (e.g., very small and uncertain new lesions; cystic changes or necrosis in existing lesions), treatment may continue until the next scheduled assessment. If at the next scheduled assessment, progression is confirmed, the date of progression should be the earlier date when progression was suspected.

10.1.3.2. Objective Response Assessment

Assessments will be based on the definitions provided in [Table 13](#) and [Table 14](#).

Table 13: Time Point Response for Patients with Target (+/- Non-Target) Disease

Target Lesions	Non-Target Lesions	New Lesions	Objective Response
CR	CR	No	CR
CR	Non-CR/Non-PD or Not all evaluated	No	PR
PR	Non-PD or Not all evaluated	No	PR
SD	Non-PD or Not all evaluated	No	SD
Not all evaluated	Non-PD	No	Not evaluable
PD	Any	Yes or No	PD
Any	PD	Yes or No	PD
Any	Any	Yes	PD

Abbreviations: CR = complete response; PD = progressive disease; PR = partial response; SD = stable disease

Table 14: Time Point Response for Patients with Only Non-Target Disease

Non-Target Lesions	New Lesions	Objective Response
CR	No	CR
Non-CR/Non-PD	No	SD
Not all evaluated	No	Not evaluable
Unequivocal PD	Yes or No	PD
Any	Yes	PD

Abbreviations: CR = complete response; PD = progressive disease; SD = stable disease

10.1.4. Best Objective Response Assessment for Solid Tumors

The best objective response for solid tumors will be assessed as defined in the Statistical Analysis Plan (SAP) per RECIST guideline (version 1.1, 2009). To be assigned a status of PR or CR for Phase 1 Expansion and Phase 2, changes in tumor measurements in patients with responding tumors must be confirmed by repeat studies that should be performed at 4 weeks after the criteria for response are first met. On the other hand, confirmation is not required for Phase 1 Dose Escalation. In the case of SD, measurements must have met the SD criteria at least once after study entry at a minimum interval of 6 weeks across the phases.

10.2. Efficacy Assessment for Brain Tumors

10.2.1. Method of Imaging

Patients with brain tumors will be evaluated for response by contrast MRI (e.g., Gd-MRI). All MRIs should be performed when the patient is on a stable dose of steroids. Gd-MRI will be performed at screening, end of every 2 cycles (up to + 2 weeks) in the first 4 cycles and every 3 cycles (\pm 7 days) thereafter and at study completion for tumor measurements. For patients who discontinued treatment for reasons other than disease progression, tumor assessments should be continued until radiologic disease progression or initiation of new anticancer therapy (whichever occurs first).

10.2.2. Tumor Definitions

[figure not shown]
10.2.2.1. Measurable and Non-measurable Contrast Enhancing Lesions

Measurable Lesions/Target Lesions

To evaluate changes in brain tumors using the RANO criteria, weighted images will be measured and monitored for response over time for up to 5 enhancing lesions identified on baseline T1 (T1 relaxation time constant). In general, the largest enhancing lesions that lend themselves to repeated measurements will be selected as target lesions (see [Figure 4](#)). Selected target lesions will demonstrate contrast enhancement, have clearly defined margins, have two perpendicular diameters of at least 10 mm, and be visible on two or more axial slices that are at most 5 mm apart with no interslice gap. If slices were thicker than 5 mm, the selected lesions should measure two times the slice thickness on the baseline scan. To perform the size measurement, the

maximal tumor diameter will be obtained with a second diameter obtained at a right angle to the first. The product of these measurements will be used for purposes of comparison between imaging time points.

Figure 4: Algorithm for Selection of Target Lesions: RANO Criteria

Non-measurable Lesions

Non-measurable lesions are generally those that do not meet the above criteria. Tumors around a cyst or surgical cavity will also be considered non-measurable unless a nodular component measuring 10 mm or greater in diameter is present.

10.2.2.2. Non-enhancing Lesions

Non-enhancing lesions visualized with T2-weighted fluid-attenuated inversion recovery (T2/FLAIR) will also be assessed when evaluating tumor response. Non-enhancing lesions will not be measured, but instead will be monitored for changes in size. It is important to note that the extent of the non-enhancing component of the tumor can be difficult to determine since localized swelling and damage caused by radiation have a similar radiographic appearance. Changes in T2/FLAIR signal that suggest presence of an infiltrating tumor include mass effect, infiltration of the cortical ribbon, and location outside of the radiation field.

10.2.3. Response Definitions

Brain tumor response to therapy will be categorized into one of four categories: complete response, partial response, stable disease, or progression.

Complete Response

Complete response (CR) will be achieved if all enhancing (measurable and non-measurable) lesions have disappeared for at least 4 weeks, there are no new lesions, and non-enhancing lesions have either improved or remain stable. Clinically, subjects must be off corticosteroids (or be receiving only physiological replacement doses) and show stable or improved clinical symptoms.

Partial Response

Partial response (PR) will be achieved when all of the following requirements are met: the sum of the products of perpendicular diameters of all enhancing lesions is reduced by 50% or more (from baseline) for at least 4 weeks, there are no new lesions, there is no progression in non-measurable lesions, and non-enhancing lesions have either improved or remain stable. Clinically, subjects must be on a corticosteroid dose no greater than the dose they were receiving at the time of the baseline scan and they must show stable or improved clinical symptoms.

Stable Disease

A subject will be considered to have stable disease (SD) if all of the following are met: the subject does not qualify for complete response, partial response, or progressive response (described below), and non-enhancing T2/FLAIR lesions are stable. Subjects must be on either a lower dose of corticosteroids or be maintaining the same dose level as baseline. Clinical symptoms must also be stable.

Progressive Disease

Progressive disease (PD) will be defined by the occurrence of any of the following:

- The sum of the products of perpendicular diameters of enhancing lesions is increased by 25% or more compared with the smallest tumor measurement obtained either at baseline or the time point with the best response for patients receiving either stable or increasing doses of corticosteroids.
- There is a significant increase in T2/FLAIR non-enhancing lesions compared to baseline or best response scans for patients receiving either stable or increasing doses of corticosteroids. The increase in T2/FLAIR non-enhancing lesions should not be attributable to other non-tumor causes (e.g., radiation therapy, demyelination, ischemic injury, etc.).
- Appearance of new lesions.
- Clear progression of non-measurable lesions.
- There is clear clinical deterioration that is not attributable to other causes apart from the tumor (e.g., seizures, medication adverse effects, complications of therapy, cerebrovascular events, etc.) or changes in corticosteroid use.
- Failure to return for evaluation as a result of death or deteriorating condition.

A summary of brain tumor response definitions (RANO) is shown in [Table 15](#).

Table 15: Summary of RANO Response Criteria

Criterion	Complete Response	Partial Response	Stable Disease	Progressive Disease
T1 enhancing disease	None	≥ 50% ↓	< 50% ↓ but <25% ↑	≥ 25% ↑ ¹
T2/FLAIR	Stable or ↓	Stable or ↓	Stable or ↓	↑ ¹
New lesion	None	None	None	Present ¹
Corticosteroids	None	Stable or ↓	Stable or ↓	NA ²
Clinical status	Stable or ↑	Stable or ↑	Stable or ↑	↓ ¹
Requirement for response	All	All	All	Any ¹

Abbreviations: NA=not applicable, RANO = Response Assessment in Neuro-Oncology

¹ Progression occurs when this criterion is present.

² Increase in corticosteroids alone will not be taken into account in determining progression in the absence of persistent clinical deterioration.

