12.2.2. Efficacy Analysis

Tumor assessments will be performed as per [Section 9.17](#), Tumor Assessments/Scans. For the Phase 1 Expansion, the primary endpoint is ORR (and EPR for primary CNS tumors), and secondary endpoints are DCR, DOR, PFS, OS.

For Phase 2, the primary endpoint is ORR and the secondary endpoints are DOR, DCR, PFS, PROs and OS (response evaluations based on independent review of images by the Core Imaging Laboratory). In addition, sensitivity analyses for some key efficacy endpoints (notably ORR and PFS) will be performed based on assessments by the investigator or local radiologist.

Response assessments will be made based on RECIST guidelines (version 1.1, 2009) for solid tumors (see [Section 10.1](#), Efficacy Assessment for Solid Tumors) or RANO for brain tumors (see [Section 10.2](#)).

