12.2.2.4. Progression-free Survival

Progression-free survival (PFS) is defined as the time from the day of the first dose to the date of first objectively documented disease progression or death (any cause), whichever occurs first. Patients who die without a reported disease progression will be considered to have progressed on the date of their death. Patients who did not progress or die will be censored on the date of their last tumor assessment. Patients who did not have any on-study assessments and did not die will be censored on the first dosing date. Patients who started any subsequent anti-cancer therapy without a prior reported progression will be censored at the last tumor assessment prior to initiation of the subsequent anti-cancer therapy. Early progression rate (EPR) for the GBM or Grade III glioma cohort will be assessed as the progression-free rate at the end of Cycle 2.

Progression-free survival will also be analyzed as a time-to-event endpoint with the median (Kaplan-Meier estimate) and associated 95% CI (Brookmeyer-Crowley methodology) reported, along with the Kaplan-Meier estimates for PFS rates at 3, 6, 9 and 12 months and associated 95% CIs (log-log transformation methodology of Kalbfleisch-Prentice).

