#### 6.4.2. **Secondary Efficacy Analyses**

The Duration of Response (DOR) is defined as the time between the date of first response and the subsequent date of objectively documented progression of disease or death. The CR or PR will be derived based on investigators or local radiologist assessment, as well as independent review. The censoring rule is shown in Table 6.

Overall survival (OS) is defined as the time between the first dosing date and the date of death. Progression free survival (PFS) is defined as the time from the first dosing date to the date of the first documented progression or death due to any cause, whichever occurs first. The censoring rule is illustrated in Table 7.

Duration of response (DOR) and PFS will be analyzed using Kaplan-Meier product-limit estimates. Median PFS will be presented with 2-sided 95% CI if estimable. Censoring rules (table 8, Table 9) is based on the Food and Drug Administration Guidance for Industry Clinical Trial Endpoints for the Approval of Cancer Drugs and Biologics (2007). The cumulative PFS will be plotted over time. OS will be analyzed similarly if data is available.

DCR is defined as the proportion of patients with objective evidence of CR, PR, or SD, except that there is no requirement for a confirmation of an SD response. DCR will be calculated and a 2-sided Clopper—Pearson 95% CI will be constructed.

Summary tables and plots for the secondary endpoints based on Independent Review will be presented for iCCA patients by these 4 categories: with FGFR2 rearrangement, without FGFR2 rearrangement, with FGFR2 rearrangement with GEM/CIS and without FGFRi Prior Treatment, with FGFR2 rearrangement with FGFRi prior treatment.

Summary tables and plots will also be presented based on data from the Investigator Review.

Table 6. Censoring Rules for Progression-Free Survival

No.	Situation	End Date	Outcome
1	Documented PD between scheduled visits a	Date of the first assessment of the series of the tests that determined PD	PFS event
2	Death during the study in absence of PD a	Date of death	PFS event
3	Patients still on treatment without PD as of data cut-off b	Date of last tumor assessment c	Censored
4	Treatment discontinuation for other than PD or death, and no post baseline tumor assessments	Date of first dose	Censored
5	Treatment discontinuation for other than PD or death with post baseline tumor assessments	Date of last tumor assessment	Censored

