#### 6.4.3. Other Efficacy Analyses

By-patient listing to include FGFR gene status, first dose date, duration of treatment, best overall response, duration of response, and cancer sub-type will be presented for each cohort.

For cohort 2 patients, response to therapy follows the RANO (Response Assessment in Neuro-Oncology) criteria. The criteria are shown in Table 8 below:

Criterion	Complete Response	Partial Response	Stable Disease	Progressive Disease
T1 enhancing disease	None	≥ 50% ↓	< 50% ↓ but <25% ↑	≥ 25% ↑ª
T2/FLAIR	Stable or ↓	Stable or ↓	Stable or ↓	↑a
New lesion	None	None	None	Present a
Corticosteroids	None	Stable or ↓	Stable or ↓	NA b
Clinical status	Stable or ↑	Stable or ↑	Stable or ↑	↓a
Requirement for response	All	All	All	Anya

Table 8. Summary of RANO Response Criteria

Abbreviations: NA=not applicable, RANO = Response Assessment in Neuro-Oncology, T1 = T1 relaxation, T2/FLAIR = T2-weighted fluid-attenuated inversion recovery.

The response results with RANO response criteria will be compared with the response results with RECIST 1.1. The best responses with the two criteria will be used and displayed in the table output. The patient level listing will be provided.

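### Group 5: failure to return because of deterioration is progression under Protocol 10.2.3 but censored at first dose under Protocol 12.2.2.4; this raises Kaplan-Meier PFS and, depending on an unstated estimator, EPR

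*Protocol*

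**What the plan says.** Protocol 10.2.3 lists the criteria for progressive disease in brain tumours, any one of which is sufficient. One is clear clinical deterioration attributable to the tumour. Another is "Failure to return for evaluation as a result of death or deteriorating condition". Neither needs an image. The Phase 1 Expansion SAP applies these criteria to Group 5, which it calls cohort 2: "For cohort 2 patients, response to therapy follows the RANO (Response Assessment in Neuro-Oncology) criteria" (6.4.3).

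Protocol 12.2.2.4 defines the PFS event by the "date of first objectively documented disease progression or death (any cause), whichever occurs first". Two handling rules follow:

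- Deaths: "Patients who die without a reported disease progression will be considered to have progressed on the date of their death".
- Living patients without a scan: "Patients who did not have any on-study assessments and did not die will be censored on the first dosing date".

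The same paragraph says that EPR "will be assessed as the progression-free rate at the end of Cycle 2". EPR is primary alongside ORR for primary CNS tumours (Protocol 6.2 and 12.2.2; Expansion SAP 3.1.1 and 3.2.1).

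Expansion SAP Table 6, row 4, censors at first dose in this situation: "Treatment discontinuation for other than PD or death, and no post baseline tumor assessments". Row 1 dates a progression from the assessment that showed it.

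Protocol 9.17.2 places the first post-baseline MRI at the end of Cycle 2, with up to two further weeks allowed.

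**The concern.** One living Group 5 patient who worsens and does not come back for the Cycle 2 MRI is a progression in one section and leaves the analysis at first dose in another. No visible passage says which rule governs.

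The timing makes this matter. The first MRI coincides with the EPR landmark, so a patient who fails before it will usually have no post-baseline scan. These are the early failures that a progression-free rate at the end of Cycle 2 is meant to count. Censoring them at first dose treats the reason for their absence as uninformative, when the protocol itself treats that reason as progression. What is at stake is the Group 5 PFS estimate and possibly a co-primary endpoint. The title of the Group 5 two-stage design also names early progression, so the classification could bear on a stage decision.

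**Working it through.** **The rules applied to one patient.** Take a Group 5 patient who is alive, has had no post-baseline MRI, and fails to return because of deterioration before the end of Cycle 2 (2 × 21 = 42 days).

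1. Protocol 10.2.3: PD, no scan required.
2. Protocol 12.2.2.4: no objectively documented progression, no death and no on-study assessment, so censored at first dose.
3. Expansion SAP Table 6: the outcome depends on the recorded reason for stopping. Protocol 7.3.1 lists clinical progression as a reason separate from RANO-defined progression. If the site records the former and it is not treated as PD, row 4 censors at first dose. If the stop is treated as PD, row 4 does not apply, but row 1 supplies no event date because there was no assessment.

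Only the deterioration limb conflicts within the protocol; a death is an event in both sections.

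**Direction.** The plan gives no figure to reproduce: Group 5 sample size, rates and boundaries are redacted. Let n be patients treated, e other progressions or deaths by the end of Cycle 2, and m the non-returners described above, with no other early censoring.

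- Counted as events: (n − e − m)/n
- Censored at first dose (Kaplan-Meier): (n − e − m)/(n − m)
- Difference: m(n − e − m)/[n(n − m)]

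The difference is positive whenever m > 0 and at least one patient is progression-free. It is zero when m = 0.

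**Size, for illustration only.** All of n, e and m are assumed. With n = 20 and e = 7 (35%):

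| m | Event | Censored at first dose | Difference (points) |
|---|---|---|---|
| 0 | 13/20 = 65.0% | 13/20 = 65.0% | 0 |
| 2 | 11/20 = 55.0% | 11/18 = 61.1% | 6.1 |
| 3 | 10/20 = 50.0% | 10/17 = 58.8% | 8.8 |
| 4 | 9/20 = 45.0% | 9/16 = 56.25% | 11.25 |

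For n = 15, 20 or 25, with e at 35% rounded and m from 1 to 4, the difference runs from 2.5 points (n = 25, m = 1: 15/25 = 60.0% against 15/24 = 62.5%) to 14.5 points (n = 15, m = 4: 6/15 = 40.0% against 6/11 = 54.5%). A Kaplan-Meier run with n = 20, e = 6, m = 2 gave 0.667 against 0.600, matching 12/18 and 12/20.

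**EPR.** The result depends on the estimator. With n = 20, e = 7, m = 2:

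- Kaplan-Meier with PFS censoring: 11/18 = 61.1%.
- Crude proportion of all treated patients, non-returners as failures: 11/20 = 55.0%, so no inflation.
- Crude proportion, non-returners as progression-free for want of documented PD: 13/20 = 65.0%.

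**The case against.** A reader might infer three stronger conclusions. The documents do not support them.

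*The plan inflates the co-primary EPR.* This needs Kaplan-Meier with the PFS censoring rules, and neither document says EPR is estimated that way. Expansion SAP 3.2.1 groups EPR with ORR, 6.4.1 gives no EPR method, and 6.1 reports binary data as percentages of the study population. The efficacy population is all treated patients (5.3). The Group 5 design is multinomial and two-stage, which suggests counting patients by category, and its redacted text may hold a counting rule. This objection stands, so the EPR claim is conditional. It does not settle the matter: EPR is defined inside the PFS paragraph, and a denominator of all treated patients does not say how non-returners are counted.

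*SAP Table 8 removes the failure-to-return criterion.* It does not. Table 8 reproduces Protocol Table 15, which also has no such line, and both keep worsening clinical status as sufficient for PD.

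*Table 6 row 4 flatly contradicts Protocol 10.2.3.* Row 4 is limited to stops for reasons other than PD or death. If the non-return is accepted as PD, the row does not apply. The conflict there depends on coding. The sentence in Protocol 12.2.2.4 has no such limit.

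The affected group may also be small. Patients enter at ECOG 0 or 1, and Protocol 9.17.2 and 10.2.1 ask for continued MRI after stopping for reasons other than progression. Four such patients out of 15 would be 27%, a frequency no document supports. Deaths are events under Protocol 12.2.2.4, although Table 6 footnote a counts an off-treatment death only within 21 days of the last dose.

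**Conclusion.** The inconsistency between Protocol 10.2.3 and Protocol 12.2.2.4 is real and rests on the text alone. Followed as written, 12.2.2.4 biases Group 5 Kaplan-Meier PFS upward, relative to the protocol's own definition of progression, whenever a living patient fails to return because of deterioration before any scan. Expansion SAP Table 6 does the same if the stop is coded as other than PD, and otherwise leaves the event undated.

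For EPR the same bias follows only if EPR uses the PFS censoring rules. A proportion over all treated patients with non-returners counted as failures would be free of it. The visible text does not say which applies.

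The actual size is unknown. The 55% against 61% comparison assumes 20 patients, 7 progressors and 2 non-returners; none of these comes from the documents.

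**What to change.** Reconcile Protocol 12.2.2.4 and Expansion SAP Table 6 with Protocol 10.2.3:

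1. State that, for Group 5, a RANO progression by clinical deterioration, or by failure to return because of deterioration, is a PFS and EPR event dated at the documented deterioration.
2. Limit first-dose censoring to patients who lack scans for other reasons.
3. In Expansion SAP 6.4.1, state that EPR uses all treated Group 5 patients as the denominator and counts these patients as progressed. If the redacted Group 5 design already has a counting rule, the two must match.
4. In the same edit, update the EPR sentence in Protocol 12.2.2.4, which still names the GBM or Grade III glioma cohort, to the current Group 5 population.

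The cost is protocol and SAP wording, plus confirmation that the reason for a missed MRI and the date of deterioration are available in the data. The downside is that the EPR and PFS figures may be slightly less favourable.
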